7.6.8 QUALITY OF LIFE OUTCOMES

Health related quality of life will be evaluated using the SF 36 that provides weightings for quality adjusted life year (QALYs). The SF 36 captures health states based on the following domains: 1) mobility; 2) self-care; 3) usual activities; 4) pain and 5) anxiety or depression. We will calculate scores using the established methodology to determine if there is a statistically significant difference in the incremental cost per QALY change across the 5 arms.

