7.6.9 HEALTH RESOURCE UTILIZATION

At Visits 2 and 3, we will ask participants to report any visit to: 1) health care professionals; 2) admissions or visits to hospital; and 3) laboratory work using the health resource utilization questionnaire. This questionnaire has been previously described and supported in previous studies [Neumann PJ, Goldie SJ, Weinstein MC: Preference-based measures in economic evaluation in health care. Annual review of public health. 2000, 21: 587-611. 10.1146/annurev.publhealth.21.1.587.]. We will estimate total health care related costs over the 12 months from a Canadian health care system

perspective. Participants will be instructed to specify total health care expenditure and report the reason for each item. Additionally, participants will be instructed to report health care expenditure due to any adverse events associated with our study. On a per participant basis, costs will be assigned to health care resource utilization using a fully allocated hospital cost model (for in-patient costs) and provincial guides to medical fees (for outpatient costs). Case analyses will consider the costs of all health care resource use and our sensitivity analyses will include only intervention related health care resource costs and a complete case analysis.

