8. ANALYSIS

Analysis, planned analysis, frequency of analysis, and correction for multiple testing

Analysis will be conducted as intention to treat and as per-protocol analysis. For the primary endpoint (ADAS-Cog plus), the change from baseline to six months and 12 months will be assessed using a repeated measures analysis of covariance (ANCOVA) model incorporating the baseline values as covariates. Observing a statistically significant difference in the primary outcome will be considered preliminary evidence of efficacy. Additionally, reduction of prevalence rate of abnormal ADAS-Cog plus score (dichotomous variable) will be assessed as a primary outcome.

We will also report variances, co-variances, and effect sizes, as well as sampling feasibility (i.e., ease of recruitment, recruitment rate, withdrawal rate). Descriptive statistics for demographic and baseline characteristics will be provided with means and standard deviations, or medians and the interquartile range where appropriate, for continuous characteristics and frequencies and percentages for categorical variables.

If the within-group comparison is statistically significant, Tukey's multiple comparisons will identify significant pairwise differences. Similarly, for the secondary endpoints, six month changes in gait performance and secondary cognitive outcomes of interest will be performed using one way analyses of variance. For group comparisons that are statistically significant, pairwise comparisons will be made using Tukey's multiple comparisons tests. All statistical tests will be two-tailed, and a *p*-value of less than 0.05 will be considered to indicate statistical significance. All calculations will be made using SPSS software package version 23.0 (SPSS Inc., Chicago, IL).

Secondary analyses will be also performed according to an intention-to-treat principle and per protocol analysis. Frequency of the analyses: preliminary analysis will be performed at month 6 to ascertain descriptive characteristics at baseline assessment. Final efficacy analysis will be performed at the end of the trial since no safety issues are involved in this study. The statistical significance of the results will be

determined by Hochberg's variation of the Bonferroni procedure for multiple testing.³⁹ An economical analysis will be also performed addressing health resources utilization.

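### Significance of incremental cost per QALY across five arms is planned with no comparator or inference method, for a ratio that cannot be ordered and behaves badly near a zero QALY difference

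*Combined protocol and SAP*

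**What the plan says.** Protocol section 7.6.8 takes QALY weights from the SF-36 and states the aim: to "determine if there is a statistically significant difference in the incremental cost per QALY change across the 5 arms". The only method given there is "We will calculate scores using the established methodology", which concerns scoring.

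Section 7.6.9 sets the cost horizon: "We will estimate total health care related costs over the 12 months". Its collection times are narrower: "At Visits 2 and 3, we will ask participants to report any visit to" health professionals, hospitals and laboratories. Visit 2 is baseline and Visit 3 is month 6. The only robustness checks are that "sensitivity analyses will include only intervention related health care resource costs and a complete case analysis".

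Section 8 adds one sentence, "An economical analysis will be also performed addressing health resources utilization", and a general two-tailed 0.05 rule. It assigns one-way ANOVA and Tukey comparisons to gait and secondary cognitive outcomes, not to the economic analysis.

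The SAP lists the SF-36 in Table 1 but includes no quality-of-life or economic outcome in section 9. Section 10.3 leaves the analysis of secondary outcomes to later work.

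**The concern.** The stated target is a p-value on a ratio, and three features of that ratio make the p-value hard to use.

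- It belongs to a pair of arms. No arm, and no participant, has an incremental cost per QALY of its own, so five arms do not supply five values to compare until a comparator is named.
- Its values have no consistent order. Equal ratios can mean opposite things, and a negative ratio can mean the best or the worst outcome.
- Its denominator is an estimated difference. When that difference may be near zero or change sign, the estimate becomes very unstable and the usual large-sample interval loses coverage.

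At stake is the cost-effectiveness statement the trial would publish. With no method fixed, the comparator and the inference could be chosen after the results are known, and a significant or non-significant ratio could be read as evidence about value that it does not carry.

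**Working it through.** **Plan's own figure.** There is none to reproduce. The documents give no QALY difference or SD, no cost difference or SD, no threshold and no power for the economic analysis.

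**Step 1: ordering (no trial data needed).** Take a cost difference of 1,000 and a QALY difference of 0.02, with either sign.

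- Dearer and better: +1,000 / +0.02 = 50,000. Cheaper and worse: −1,000 / −0.02 = 50,000. The ratios are equal and the meanings opposite.
- Dearer and worse: +1,000 / −0.02 = −50,000. Cheaper and better: −1,000 / +0.02 = −50,000. Again the ratios are equal and the meanings opposite.

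Net monetary benefit, threshold × QALY difference − cost difference, separates them. At a threshold of 50,000 the second pair gives −1,000 − 1,000 = −2,000 and +1,000 + 1,000 = +2,000. The first pair gives values of equal size and opposite sign at every threshold except 50,000, where both are zero.

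**Step 2: how often the estimated QALY difference has the wrong sign.** From the protocol: 34 evaluable per arm (section 5.3: 40 recruited less 15% dropout). Assumed: QALY SD 0.05 to 0.15, true gain 0.01 to 0.05, normal estimates.

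SE = SD × √(2/34), and P(wrong sign) = Φ(−gain/SE). For example, with SD 0.10, SE = 0.10 × 0.2425 = 0.0243; at gain 0.01, Φ(−0.412) = 0.340.

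A 95% Fieller set for the ratio is unbounded when the QALY difference is itself not significant, so P(unbounded) = Φ(1.96 − gain/SE) − Φ(−1.96 − gain/SE).

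| QALY SD | SE | True gain | P(wrong sign) | P(Fieller set unbounded) |
|---|---|---|---|---|
| 0.05 | 0.0121 | 0.01 | 0.205 | 0.869 |
| 0.05 | 0.0121 | 0.02 | 0.050 | 0.622 |
| 0.05 | 0.0121 | 0.05 | 0.000 | 0.015 |
| 0.10 | 0.0243 | 0.01 | 0.340 | 0.930 |
| 0.10 | 0.0243 | 0.02 | 0.205 | 0.869 |
| 0.10 | 0.0243 | 0.05 | 0.020 | 0.460 |
| 0.15 | 0.0364 | 0.01 | 0.392 | 0.941 |
| 0.15 | 0.0364 | 0.02 | 0.291 | 0.915 |
| 0.15 | 0.0364 | 0.05 | 0.085 | 0.721 |

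For SD 0.05 to 0.10 and gain 0.01 to 0.02, the wrong-sign range is 5% to 34%. With all 40 per arm it is 4% to 33%.

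**Step 3: simulation at 34 per arm.** Further assumptions: cost difference 1,000, cost SD 5,000, normal costs independent of QALYs, the same gain in arms 1 to 4, threshold 50,000.

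- At SD 0.10 and gain 0.02 the true ratio is 1,000 / 0.02 = 50,000. The central 95% of estimates ran from about −572,000 to +606,000.
- At SD 0.10, at least one of the four contrasts with arm 5 had a negative QALY difference in 64% of trials at gain 0.01 and 45% at gain 0.02.
- Coverage of nominal 95% intervals at SD 0.10:

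| True gain | Symmetric interval on ratio | Fieller set | Net monetary benefit |
|---|---|---|---|
| 0.01 | 77.2% | 95.1% | 95.3% |
| 0.02 | 92.3% | 94.9% | 94.9% |
| 0 | not defined | not defined | 95.0% |

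**Step 4: time periods.** The SF-36 is scheduled at baseline, month 6 and month 12 (protocol sections 7.2, 7.3 and 7.5), so QALYs can span 12 months. The resource questions are asked at baseline and month 6, and neither visit table lists the questionnaire. The call three months after the intervention (section 6.1) tracks emergency visits and medication changes, but it is not the costing questionnaire. Months 6 to 12 are therefore not covered by the stated cost collection.

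**The case against.** The strongest reply is that the protocol has not committed itself to a bad test. It names no test at all. Section 3 calls arm 5 the pure control arm and SAP section 10.2 uses it as the reference for the primary outcome, so four ratios against arm 5 are a natural reading. Fieller sets are valid for each of them. This is right as far as it goes. A reader might infer that no valid inference exists for this ratio, or that the trial will produce an arbitrary result; the documents support neither. Fieller sets held their coverage in the check above, and the method that failed, a symmetric interval on the ratio, is nowhere specified.

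A reader might also infer that the QALY difference will be close to zero. The documents give nothing to establish that, and the size of the problem depends on it. The 34 per arm is itself derived from 20-week dropout, so the 12-month number could be lower.

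The stakes are also limited. No hypothesis in section 2.1 concerns cost, section 4.2 lists quality-of-life scores but not cost-effectiveness, and no adoption decision is tied to the result.

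What remains is that the comparator is unstated for costs, the method is unstated everywhere, and reading arm 5 as the comparator does not cure the lack of order shown in step 1. Fieller sets, though valid, would often be unbounded over much of the assumed range.

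**Conclusion.** The concern holds as an ill-defined inferential target with no method attached. That part needs no assumed inputs: the ratio is a property of a contrast, and equal ratios can carry opposite meanings. The mismatch between 12-month costs and the two collection visits can likewise be read directly from section 7.6.9.

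The numerical instability is conditional. At 34 per arm, with assumed QALY SDs of 0.05 to 0.10 and gains of 0.01 to 0.02, the wrong-sign probability is 5% to 34%. At SD 0.05 and gain 0.05 it is close to zero and the Fieller set is unbounded in only 1.5% of trials.

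The weight is minor. This is a secondary economic analysis outside the SAP, and it does not touch the primary efficacy conclusion.

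**What to change.** In section 7.6.8, or in the later plan for secondary outcomes, replace the significance test on the ratio with incremental net monetary benefit:

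- Name the contrasts: arms 1 to 4, each against arm 5.
- For each participant compute threshold × QALY − cost, over a stated range of willingness-to-pay values.
- Regress on arm with baseline utility as covariate. Give bootstrap 95% confidence intervals and cost-effectiveness acceptability curves.
- Report the cost-per-QALY ratio descriptively, or with Fieller or bootstrap intervals, and say what is reported when the QALY difference is zero or negative.
- Compute costs and QALYs over the same period. Reconcile section 7.6.9 with its own collection times: either document resource use for months 6 to 12 or limit both quantities to the period that was collected.

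The change of target costs a little analysis work and the need to state and defend a threshold range. It needs no change to the trial design. A 12-month version does need resource-use data for the second half-year; if these were not collected, the horizon has to be shortened and the report should say so.

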7.6.9 HEALTH RESOURCE UTILIZATION

At Visits 2 and 3, we will ask participants to report any visit to: 1) health care professionals; 2) admissions or visits to hospital; and 3) laboratory work using the health resource utilization questionnaire. This questionnaire has been previously described and supported in previous studies [Neumann PJ, Goldie SJ, Weinstein MC: Preference-based measures in economic evaluation in health care. Annual review of public health. 2000, 21: 587-611. 10.1146/annurev.publhealth.21.1.587.]. We will estimate total health care related costs over the 12 months from a Canadian health care system

perspective. Participants will be instructed to specify total health care expenditure and report the reason for each item. Additionally, participants will be instructed to report health care expenditure due to any adverse events associated with our study. On a per participant basis, costs will be assigned to health care resource utilization using a fully allocated hospital cost model (for in-patient costs) and provincial guides to medical fees (for outpatient costs). Case analyses will consider the costs of all health care resource use and our sensitivity analyses will include only intervention related health care resource costs and a complete case analysis.

8. ANALYSIS

Analysis, planned analysis, frequency of analysis, and correction for multiple testing

Analysis will be conducted as intention to treat and as per-protocol analysis. For the primary endpoint (ADAS-Cog plus), the change from baseline to six months and 12 months will be assessed using a repeated measures analysis of covariance (ANCOVA) model incorporating the baseline values as covariates. Observing a statistically significant difference in the primary outcome will be considered preliminary evidence of efficacy. Additionally, reduction of prevalence rate of abnormal ADAS-Cog plus score (dichotomous variable) will be assessed as a primary outcome.

We will also report variances, co-variances, and effect sizes, as well as sampling feasibility (i.e., ease of recruitment, recruitment rate, withdrawal rate). Descriptive statistics for demographic and baseline characteristics will be provided with means and standard deviations, or medians and the interquartile range where appropriate, for continuous characteristics and frequencies and percentages for categorical variables.

If the within-group comparison is statistically significant, Tukey's multiple comparisons will identify significant pairwise differences. Similarly, for the secondary endpoints, six month changes in gait performance and secondary cognitive outcomes of interest will be performed using one way analyses of variance. For group comparisons that are statistically significant, pairwise comparisons will be made using Tukey's multiple comparisons tests. All statistical tests will be two-tailed, and a *p*-value of less than 0.05 will be considered to indicate statistical significance. All calculations will be made using SPSS software package version 23.0 (SPSS Inc., Chicago, IL).

Secondary analyses will be also performed according to an intention-to-treat principle and per protocol analysis. Frequency of the analyses: preliminary analysis will be performed at month 6 to ascertain descriptive characteristics at baseline assessment. Final efficacy analysis will be performed at the end of the trial since no safety issues are involved in this study. The statistical significance of the results will be

determined by Hochberg's variation of the Bonferroni procedure for multiple testing.³⁹ An economical analysis will be also performed addressing health resources utilization.

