5. Pre-existing or current active participation in physical activity program involving aerobic or resistance training regimen in previous 6 months.
6. Taking Cognitive enhancers, Neuroleptics, Anticholinergics, or Vitamin D in doses more than 1000IU/day or equivalent.
7. Known hypercalcemia and/or disorder that is cause of hypercalcemia (e.g. hyperparathyroidism/ Paget's disease/ Sarcoidosis).
8. Known renal/kidney insufficiency.
9. Uncontrolled hypertension.
10. Uncontrolled diabetes.

5.3 SAMPLE SIZE:

Sample size calculation is based on changes in our main primary outcome: stabilization/improvement in cognition as measured using the **Alzheimer Disease Assessment Scale Cognitive Plus** (ADAS-Cog Plus). We expect a change of three (3) points on the ADAS-Cog Plus scores, a value that is considered clinically significant, and it is similar in magnitude to the improvements seen in positive pharmacological clinical trials in dementia.[26] Two previous studies testing the effect of exercises on cognition in 200 MCI participants shown a mean score of 6-7 and a standard deviation of 3 in the ADAS-Cog.[24,31] Based on these data and assuming a mean change of 3 points in the ADAS-Cog, 34 participants per arm are required to have 80% power to detect a change of three points or more on the ADAS-Cog with a 2-tailed α error of 5%, adjusted for 10 potential pairwise comparisons. We estimate a worst case scenario of 15% of dropout rate during the 20 weeks of follow up to the main endpoint. Therefore, we will aim to recruit 40 per arm for a total of 200 participants.

Sample size estimates per group for the primary outcome: change in ADAS-Cog Plus

	Type I error=0.05	Type I error=0.01	Type I error=0.001
Power=80%	34	50	59
Power=90%	51	54	70
Power=99%	68	82	102

Reference: Independent Groups - Machin D, Campbell M, Fayers, P, Pinol A (1997) Sample Size Tables for Clinical Studies Second Ed. Blackwell Science ISBN 0-86542-870-0 p. 24-25

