7.2 BASELINE EVALUATION (VISIT 2)

Participants will undergo rigorous baseline evaluations, which will take place up to four weeks after the screening session. Baseline assessments will include neuroimaging, neuropsychological, and gait measures. These will be repeated at the 6-month and 12-month follow-up.

1. Log return of the Physical Activity Device
2. Blood Draw
3. Clinical Medical Questionnaire
4. Quality of Life Questionnaire (SF-36)
5. ADAS-Cog Plus Tests (ADAS-Cog 13 Tests, plus the Digit Span Forward and Backward WAIS-III, TMT A and B, Digit Symbol Test, Boston Naming Test)
6. D-KEFS Colour Word Interference Test
7. Short Physical Performance Battery (SPPB)
8. Six Minute Walk Test (6MWT)
9. Dual task control assessment while seated (mental task)
10. Gait assessment using Gait Mat and Accelerometers (when available)
11. Schedule Neuroimaging

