153 AP/PA correction scan = 7 min) to calculate fractional anisotropy and diffusivity in white
154 matter tracts as well as derive tract-based statistics. Cerebrovascular integrity and
155 pathology will be assessed using the following contrasts: PD/T2 = 5 min; FLAIR = 7 min,
156 and T2* = 5 min). Functional magnetic resonance imaging at rest (rsfMRI plus field map
157 = 12 min) will also be acquired to measure change in data-driven functional networks.

158 **9.5 Change in Blood biomarkers measures**

159 Serum biomarkers of inflammation (C reactive protein, and interleukin 6), neuroplasticity
160 (brain-derived neurotropic factor), endothelial health (vascular endothelial growth factor
161 1), and vitamin D serum levels will be measured before and after intervention.

162 **9.6 Covariates**

163 Pre-specified covariates will be age, sex, years of education and number of
164 comorbidities.

165

166 **10. Statistical Analysis**

167 **10.1 Descriptive Analysis**

168 The baseline characteristics will be summarized using means and standard deviation, or
169 medians and interquartile range where appropriate, for continuous characteristics, and
170 frequencies and percentages for categorical variable.

171 **10.2 Primary Efficacy Analysis**

172 The primary analysis will be based on the intention-to-treat principle, including everyone
173 who were randomized. Comparisons between arms will be conducted according to pre-
174 specifications in the protocol. These comparisons align well with the recommended
175 analysis and reporting of factorial trials⁵, which used “inside the table” and “at the
176 margin” analyses for different comparisons. The “inside the table” analysis will be used
177 to compare each intervention effect to control, while “at the margins” analysis will be
178 used to assess the effect of adding intervention.

179 The major interest would be the effect of the intervention on change in primary
180 outcomes at 6 Month compared to the control arm (arm 5). The primary outcome
181 measure of mean change in ADAS-Cog-13 and ADAS-Cog-Plus scores will be analyzed
182 using a linear mixed model with restricted likelihood estimation. The model will be fitted
183 with participant-specific random intercept and fixed effects of time, intervention arm, and
184 time x intervention arm interaction. The time variable will be used as a categorical
185 variable (0 = baseline; 1 = Month 6.) The intervention arm variable will be dummy

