243 exercise and vitamin D intervention (arm 1 and 3) and pooling the intervention arms
244 providing exercise intervention but not vitamin D (arm 2 and 4). A new independent
245 variable will be created to represent addition of vitamin D: both aerobic-resistance
246 exercise and vitamin D intervention (pooled arm 1 and 3) and aerobic-resistance
247 exercise but no vitamin D intervention (pooled arm 2 and 4). The linear mixed model will
248 be repeated using this new independent variable and the two pooled arms will be
249 compared. This will allow to explore whether adding vitamin D to aerobic-resistance
250 exercise improve the outcome compared to the aerobic-resistance exercise. If a
251 significant difference is observed, the two pooled arms will be compared to the control
252 arm (arm 5) to assess the main effect.

253 10.2.4 Effect of multidomain intervention

254 The objective 4 (effect of multi-domain intervention (aerobic-resistance exercise +
255 cognitive training + Vitamin D supplement) on cognitive function) will be assessed using
256 the time x intervention arm interaction fitted in the linear mixed model in section 10.2.
257 The interaction term between time x intervention arm 1 will represents the effect of
258 multidomain intervention (arm 1) compared to the control (arm 5).

259 **10.2.5 Long-term effect: From Baseline and Post-intervention to Follow up**

260 The long-term intervention effect from baseline and post-intervention to follow-up
261 (Month 12) will be assessed using the linear mixed model. Time will be used as a
262 categorical variable (Baseline, Month 6, and Month 12). Individuals with incomplete
263 follow up assessments will still be included in the linear mixed model.

264 **10.2.6 Post-hoc analyses**

265 ADAS-Cog-Plus is a construction proposed originally by Skinner et al.⁹, adding extra
266 tests for executive function and verbal fluency to increase sensitivity to detect
267 progression from MCI to dementia. Post hoc analyses will be performed to explore the
268 effect of intervention on ADAS-Cog-Plus scores by adding individual Plus items, one by
269 one, to ADAS-Cog-13.

270 **10.3 Secondary Outcomes Analyses**

271 The secondary analysis will be performed in an intention-to-treat population and a per-
272 protocol population. The details of the statistical analysis plan for secondary outcomes
273 are not included in this analysis plan as the secondary outcome analyses will not be

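### Gait and secondary cognitive outcomes are to be tested by one-way ANOVA on change with no baseline covariate; ANCOVA would be more precise at no cost in data

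*Combined protocol and SAP*

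**What the plan says.** Protocol section 8 (Analysis) gives one sentence on the test for these endpoints: "six month changes in gait performance and secondary cognitive outcomes of interest will be performed using one way analyses of variance". Where the group comparison is significant, Tukey pairwise comparisons follow. A one-way analysis of variance has arm as its only factor, and no covariate is mentioned.

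For the primary endpoint, the same section specifies a "repeated measures analysis of covariance (ANCOVA) model incorporating the baseline values as covariates".

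SAP section 10.3 covers secondary outcomes only to say that the details "are not included in this analysis plan as the secondary outcome analyses will not be" part of the primary manuscript, and that the work will be done later. SAP section 9.6 lists the covariates: "Pre-specified covariates will be age, sex, years of education and number of" comorbidities. The baseline value of the outcome is not on that list.

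Protocol section 7.2 confirms that the needed data exist: "Baseline assessments will include neuroimaging, neuropsychological, and gait measures", and these are repeated at 6 months.

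**The concern.** Within one section, the primary outcome gets baseline adjustment and the gait and cognitive secondary outcomes do not, and no reason is given. A change score does use the baseline, but by subtracting it with a fixed coefficient of 1. ANCOVA estimates the coefficient. When the correlation between baseline and follow-up is below 1, full subtraction adds noise and over-corrects for whatever chance imbalance the arms had at baseline.

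The outcomes affected are not incidental. Memory, executive function, attention and dual-task gait appear in the second of the protocol's primary hypotheses (section 2.1.a), and SAP hypotheses 1 to 4 include secondary outcomes. No sample size is stated for any of them, and the comparisons rest on about 34 completers per arm. Avoidable variance therefore means wider intervals and lower power for contrasts that have little power to start with.

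**Working it through.** **The plan's own figure.** The documents give no power or sample size for a secondary outcome. Section 5.3 concerns the primary outcome only: "34 participants per arm are required to have 80% power to detect a change of three points or more on the ADAS-Cog". Its dropout step reproduces: 34 / 0.85 = 40 per arm. The 34 itself does not. A difference of 3, SD 3, 80% power and a two-sided alpha of 0.05/10 = 0.005 give 27 per arm by the normal approximation, or 29 by the t distribution. That is a separate matter; here 34 serves only as the expected number of completers per arm.

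**Inputs.**
- n = 34 completers per arm and 5 arms (protocol sections 3 and 5.3).
- Tukey comparisons at two-sided 5% (protocol section 8).
- Difference of 0.5 SD of change: an assumption. The SAP uses d of about 0.5 for ADAS-Cog-13; no effect size is given for the secondary outcomes.
- rho, the baseline-to-6-month correlation: not in the documents, assumed 0.3 to 0.9.
- Equal variance s² at both visits: an assumption.

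**Step 1: variances.**
- Change score: 2s²(1 − rho).
- ANCOVA: s²(1 − rho²) = s²(1 − rho)(1 + rho).
- Ratio, ANCOVA to change: (1 + rho)/2, which is below 1 whenever rho is below 1.

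In a five-arm simulation with 34 per arm (4,000 replicates), the ratio was 0.74 at rho 0.5 and 0.85 at rho 0.7, against 0.75 and 0.85 from the formula.

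**Step 2: equivalent sample size.** 34 per arm with ANCOVA matches 34 / [(1 + rho)/2] per arm with change scores. At rho 0.5, 34 / 0.75 = 45.

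**Step 3: power under the planned Tukey step.**
- Pooled degrees of freedom: 5 × 34 − 5 = 165 (one fewer for ANCOVA, with no visible effect).
- Tukey critical value on the t scale: 2.758.
- Noncentrality on change: 0.5 × √(34/2) = 2.062, giving power of 25%.
- Noncentrality with ANCOVA: 2.062 / √[(1 + rho)/2]. At rho 0.5 this is 2.062 / 0.866 = 2.380, giving 36%.

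| Assumed rho | Variance ratio | 34 per arm is worth | Tukey pairwise power, change | Tukey pairwise power, ANCOVA |
|---|---|---|---|---|
| 0.3 | 0.65 | 52 | 25% | 42% |
| 0.5 | 0.75 | 45 | 25% | 36% |
| 0.7 | 0.85 | 40 | 25% | 30% |
| 0.8 | 0.90 | 38 | 25% | 28% |
| 0.9 | 0.95 | 36 | 25% | 26% |

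**Step 4: would the SAP's primary model recover the loss?** SAP section 10.2 keeps baseline as a response row and fits time, arm and time by arm. On a simulated complete data set with two time points (34 per arm, rho 0.6), its time-by-arm contrast and the change-score contrast gave the same estimate (−0.052) and the same standard error (0.212). It recovers nothing.

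**The case against.** Several points on the other side stand.

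- **It is efficiency, not validity.** A reader might infer that the planned test is biased or inflates type I error. It does neither: under randomization the change-score contrast is unbiased. Regression to the mean matters only conditionally on a chance imbalance at baseline.
- **Scope.** A reader might extend the point to all secondary outcomes. The sentence covers gait performance and secondary cognitive outcomes. For imaging, biomarkers and SF-36, section 8 names no specific test, so the gap there is a missing specification and not an unadjusted ANOVA.
- **The analysis is deferred.** The SAP openly postpones the secondary analyses, and it has already replaced the protocol's primary method with a mixed model. The documents do not show that the ANOVA rule will be carried out; they show that it is the only rule stated for these endpoints.
- **Power on a simple two-arm test looks more dramatic.** An unadjusted two-arm t-test at 5% gives 53% on change against 65% with ANCOVA at rho 0.5. That is not the planned comparison. Under Tukey, absolute power is about half as large.
- **The gain may be small.** At rho 0.8 to 0.9 it is only 1 to 3 percentage points of Tukey power, and the outcomes are secondary and outside the primary manuscript.

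These points limit scope and size. None gives a reason to prefer the unadjusted analysis when the baseline values are in hand.

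**Conclusion.** The point holds for the continuous gait and secondary cognitive outcomes, as a free improvement in precision. The only stated test leaves out a covariate that the protocol itself uses for the primary endpoint. The cost is a change-score variance larger than that of ANCOVA by a factor of 2/(1 + rho): 33% at rho 0.5, 18% at 0.7 and 5% at 0.9. The size depends on rho, which has to be assumed, and on equal variances at the two visits; the power figures also assume a difference of 0.5 SD of change. ANCOVA does not make these contrasts well powered: even at rho 0.3, Tukey pairwise power reaches only about 42%.

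**What to change.** In protocol section 8, and in the secondary-outcome SAP still to be written, replace the one-way ANOVA with the following: each continuous gait and secondary cognitive outcome is analysed by ANCOVA, with the 6-month value as response and arm and the baseline value of the same measure as terms, and Tukey comparisons are made on the adjusted means. Site may be added as a term, since section 7.2.1 has randomization sequences generated in each site.

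If a mixed model is preferred, constrain the baseline means to be equal across arms. The SAP's time-by-arm model in its present form should not be copied for this purpose.

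The cost is a sentence or two of text. No new data, visits or participants are needed.
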